When maintained in a stable manner, at an appropriately safe distance from gut epithelial cells, the microbiota provides benefits to the host, especially in terms of energy harvest, pathogen exclusion, and promotion of immune development. In contrast, disturbance of the microbiota-host relationship can drive chronic gut inflammation that can promote an array of chronic inflammatory diseases including metabolic syndrome. While host genetics are an important determinant of the host-microbiota relationship, the dramatic increase in incidence of numerous chronic inflammatory diseases, including inflammatory bowel disease (IBD) and metabolic syndrome over the last 60 years amidst relatively constant genetics, and highlights the importance of understanding how non-genetic factors such as diet might alter the microbiota-host relationship to promote gut inflammation. Consequently, we and others have focused on how differences in macronutrient consumption influence the microbiota. However, dietary patterns can also be characterized by constituents other than macro and micronutrients. Post-mid-20th century dietary changes include consumption of an array of synthetic compounds that are added to many processed foods. The biologic effect of these food additives are not well described, particularly

their potential to influence microbiota composition and/or its interaction with the host. One particularly disconcerting class of compounds are synthetic dietary emulsifiers including polysorbate 80 (P80) and carboxymethylcellulose (CMC). These detergent-like compounds, which are incorporated into a variety of processed foods, are not well-absorbed, thus allowing them to interact with the microbiota and gut mucosa. We have recently shown that, in mice, consumption of P80 and CMC, alters microbiota composition, have pro-inflammatory potential and promote microbiota encroachment into the colonic mucosa, low-grade inflammation, and metabolic syndrome¹. However, it is not known whether these compounds have similar effects in humans. Addressing this critically important question is the central goal of this study. Our initial focus will be on CMC, which, despite not having been tested in humans and not widely studied in animals, has "generally regarded as safe (GRAS)" status from the US FDA, allowing it to be widely and unrestrictedly used in a broad variety of processed foods.

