6.1.3 Stool sample collection

Stool will be collected from the inpatient participants daily. Only the first sample of each day will be aliquoted and frozen. Subsequent samples (if available) will be weighed and the weight will be recorded. Each stool specimen that is collected will be processed in the same manner. The participant will be provided with a collection device to be placed in the commode that allows for separation of urine and feces, and keeps the feces separated from the toilet water. After they have finished voiding their first stool of the day, the specimen will be immediately processed according to the following protocol by the CHPS nurses. Using vials with small spoons attached to the lid, a small amount of stool will be scooped on to the spoon from the surface of the stool sample and leveled off with a tongue depressor. The weight of the sample will be recorded. A minimum of seven samples will be obtained from one stool collection. All samples will be labeled with the subject ID #, and the date of collection from the volunteer. The core sample will be labeled the same way. The aliquoted samples and the core sample will be immediately frozen at minus 80°C. The nurses will rate the sample based on the Bristol Stool Chart. Residual stool samples will be stored into up to five 15ml coring vials. Subsequent stools will be weighed in the collection device, rated on the Bristol Stool Chart, and then discarded.

In order to have a baseline stool sample prior to study diet, participants will be required to collect a stool sample prior to the post-screening visit. Participants will also collect a stool sample on the day prior to admission to CHPS. Study staff will provide the participant with collection materials and instructions for collecting the stool at home and bringing it in to study staff. Immediately after voiding the sample, the participant will put a small amount of stool into a spoon-top vial containing ethanol. They will label this vial and the collection device containing the remainder of the stool sample with the date of collection, and will rate the stool on the Bristol Stool Chart. They will then arrange a drop-off time with the study coordinator within 48 hours of sample collection. The study coordinator will bring this stool sample to the study lab on the 9th floor Biomedical Research Building (BRB). Lab personnel will aliquot the stool sample into a minimum of 7 spoon-top vials.

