6.2.4.6 Sample collection

Blood, urine, and feces samples will be obtained. Up to 15 ml of urine samples will be collected prior to 09:00h after an overnight fast starting at midnight. Approximately 16cc of blood will be collected for metabolomics at each collection following an overnight fast prior to breakfast. Participants will be provided a stool collection kit to collect a stool sample on the day prior to admission or on the morning of admission. The first stool sample will be weighed, aliquoted and frozen. Participants will collect stool from all subsequent bowel movements. This stool will be weighed, the weight recorded and discarded. In addition, a stool sample will be collected by the participant at home either the day prior to Visit 3 or the morning of Visit 3. Participants will bring the stool sample to the visit. Study staff will provide the participant with collection materials and instructions for collecting the stool at home and returning it to study staff (See section 6.1.3).

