6.2.5.4 Sample collection

On days 2, 3, 4, 8, and 10 blood will be obtained. Approximately 16cc of blood will be collected for metabolomics after an overnight fast prior to breakfast. Urine and feces samples will also be obtained. Up to 15 ml of urine samples will be collected prior to 09:00h after an overnight fast starting at midnight. The first stool sample will be aliquoted and frozen.

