6.4.3 Microbiome characterization

Microbiota localization. For each subject, 4 distal biopsies, collected pre/post CMC and immediately preserved in Carnoy fixative, will be assayed by fluorescence microscopy to determine bacterial localization relative to the epithelium. Specifically, for each specimen, we will examine 5 high-powered fields, selected arbitrarily while blinded to the accompanying clinical data. We will use staining protocols developed by Gunnar Hansson and colleagues^{36, 37} that we have ourselves used extensively in our recent publications^{19, 38}. For each field, we will measure the distance of the 5 closest bacteria per field as illustrated in **Figure 2**. The 25 distances (5 per field x 5 fields) will then be averaged to produce the "average closest bacteria" and compared between groups as reported in our mouse-based studies^{19, 38}. **2) Microbiota composition.** Each fecal sample will be subjected to 16S, metagenomics, and meta-transcriptomic sequence-based analysis as previously described. Sequencing via the Illumina platform (Miseq for 16S, NextSeq500 for metagenomics/transcriptomic). Data will be processed and analyzed via the Qiime platform and R software, in a manner similar to our previous publications^{19, 38-40}. **3) Microbiota pro-inflammatory potential.** For each fecal sample collected, we will measure fecal levels of bioactive flagellin and LPS as reported in our previous publications^{19, 38, 40}. Briefly, for each sample, we will prepare a soluble surface extract to be generated by bead-beating followed by centrifugation. Such samples will be diluted and then applied to cells engineered to express receptors for TLRs 4 or 5 and produce peroxidase under the control of a NF- κ B responsive promoter - our initial publication using this technique describe an extensive set of control studies we have utilized to validate this approach⁴¹. These assays, standardized with E. coli flagellin and LPS will report the levels of bioactive LPS and flagellin, which we have shown are broadly reflective of a fecal specimens ability to drive pro-inflammatory gene expression upon injection into mice⁴¹. Comparison between groups will use t-test, repeated measures ANOVA or analogous non-parametric tests.

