7.2.2 Comparison of metabolites between diets with and without CMC

The first analysis will compare the abundance of fecal and plasma metabolites between the two dietary groups. As assignment to the diet will be based on randomization, the primary analysis will be an unadjusted t-test to compare the concentration of the various metabolites measured in the plasma and feces. As there will be multiple comparisons, we will report both nominal (p values) and q values accounting for the multiple testing.

7.2.3 Effects of CMC consumption on a range of inflammatory and metabolic parameters that characterize metabolic syndrome

Weight change will be compared between the treatment groups from day 1 to day 11 using a t-test. If there is evidence of confounding despite randomization, additional analyses will use linear regression adjusted for change in weight from day 1 to day 11 and BMI at day 0.

We will also assess changes to each subject regarding satiety (from the questionnaire re food adequacy/sufficiency). These data are on visual analogue scale so will be compared using unpaired t-test for between group comparisons or paired t-tests for within group comparisons.

The area under the glucose and insulin concentration curves during the oral glucose tolerance test at day 1, day 11 and the change from day 1 to day 11 will be compared between groups using a t-test. The $\Delta I_{30}/\Delta G_{30}$ will be used as a measure of

beta cell function⁴⁵ while homeostasis model assessment of insulin resistance (HOMA-IR) will be used to estimate insulin resistance⁴⁶ and compared between the groups with a t-test at the same time points.

Sera will be assayed for a range of hormones and cytokines using a customized bead-based assay designed to include immune inflammatory and metabolic markers of obesity and type 2 diabetes (includes IL-8, IL-6, TNF α , lipocalin-2, MCP1, insulin, leptin, ghrelin, ESR, CRP) all of which are known to be elevated in metabolic syndrome (performed at GSU). Additionally, fecal samples will be assayed for lipocalin-2 by ELISA. These data will be compared using unpaired t-test for between group comparisons or paired t-tests for within group comparisons.

8 Safety and Adverse Events

Adverse Event

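### Fecal analytes are compared per unit of stool with no output or CMC-corrected analysis, so a concentration difference cannot be read as altered production when only one arm eats a poorly absorbed polymer

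*Combined protocol and SAP*

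**What the plan says.** **Scale and test.** For metabolites, section 7.2.2 states that "the primary analysis will be an unadjusted t-test to compare the concentration of the various metabolites measured in the plasma and feces", and justifies the lack of adjustment by randomisation. For LPS and flagellin, section 6.4.3 says "For each fecal sample collected, we will measure fecal levels of bioactive flagellin and LPS", then "Comparison between groups will use t-test, repeated measures ANOVA or analogous non-parametric tests". Section 7.2.3 compares fecal lipocalin-2, measured by ELISA, with t-tests. No unit or denominator is given for these last three. Section 6.1.3 describes the banked material as level spoonfuls from the first stool of the day.

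**The contrast.** Sections 3.1 and 5 keep the two diets the same except for 15 g/day of CMC in one arm; no bulk-matched control is described. Section 1.1 says of synthetic emulsifiers, naming CMC, that they "are not well-absorbed, thus allowing them to interact with the microbiota and gut mucosa". Section 7.1 expects detectable CMC in the feces of the whole treated group, and section 6.4.2 quantifies it there.

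**Stool weights.** For stools after the first of the day, section 6.1.3 says "Subsequent samples (if available) will be weighed and the weight will be recorded". For Day 1, section 6.2.4.6 says "The first stool sample will be weighed, aliquoted and frozen". For Days 2 to 10, section 6.2.5.4 says "The first stool sample will be aliquoted and frozen", and section 6.2.6.5 says the same for Day 11. Section 7.2 uses neither the weights nor the fecal CMC level to normalise any fecal analyte.

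**The concern.** A concentration is an amount divided by stool mass. If unabsorbed CMC, with any water it holds, adds to stool mass, the denominator grows in one arm only. Concentrations could then fall although gut and microbiota produce the same amounts. Randomisation does not remove this, because the assigned diet causes it.

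Two readings are at stake. A broad fall in fecal metabolites could be taken as loss of microbial products. A true rise in LPS, flagellin or lipocalin-2, the pro-inflammatory signals behind Objectives 2 and 3, could be attenuated. With the planned analysis alone, neither can be told apart from dilution.

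**Working it through.** **1. The plan's own figure.** Section 7.1 gives 80% power for 1.51 SD between groups with 8 per arm. Alpha is not stated; I take 0.05 two-sided. The exact noncentral t gives 80.2% at 1.51 SD, so the figure reproduces. The same test is used below.

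**2. Inputs.** From the documents: 15 g/day against 0, and 8 per arm. Assumed, because the documents give nothing: wet stool M = 100 to 200 g/day without CMC, all ingested CMC recovered in stool, log-scale between-person SD 0.4 to 0.6, and k grams of stool added per gram of CMC (k = 1 is polymer alone; k = 3 adds 2 g of bound water).

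**3. Formula.** With production unchanged, the concentration ratio CMC/control = M / (M + 15k), and the shift in SD units = −ln(ratio) / log-SD.

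| M, g/day | k | Ratio | Fall | Shift at log-SD 0.4 / 0.6 | Chance of p<0.05 |
|---|---|---|---|---|---|
| 100 | 1 | 100/115 = 0.870 | 13% | 0.35 / 0.23 | 10% / 7% |
| 200 | 1 | 200/215 = 0.930 | 7% | 0.18 / 0.12 | 6% / 6% |
| 100 | 3 | 100/145 = 0.690 | 31% | 0.93 / 0.62 | 41% / 21% |
| 200 | 3 | 200/245 = 0.816 | 18% | 0.51 / 0.34 | 16% / 10% |

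At 5 g of water per gram (k = 6) the fall is 31 to 47% and the chance of p<0.05 is 21 to 85%. That needs a stronger assumption, and I place no weight on it.

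**4. Attenuation.** Assume a CV of 50% (log-SD = √ln(1.25) = 0.472). The fold rise with 80% power is exp(1.51 × 0.472) = 2.04. At M = 150, k = 1, the ratio is 150/165 = 0.91 and power falls to 68%. At k = 3, the ratio is 150/195 = 0.77 and power falls to 43%.

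**5. The planned q values.** They do not guard against a shift shared by many metabolites. In a simulation of 200 metabolites with unchanged production (correlation 0.2, CV 50%, Benjamini-Hochberg 5%), the share of trials flagging at least one was 4% with no dilution, 9% at ratio 0.91 and 38% at ratio 0.77.

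**6. What the alternative scales do.** Daily output is concentration × stool mass: (A/(M + 15k)) × (M + 15k) = A, so dilution cancels. Concentration per gram of CMC-free stool is A/(M + 15k − 15). At k = 1 this is A/M, so dilution again cancels. At k = 3 it is A/(M + 30), leaving ratios of 100/130 = 0.77 to 200/230 = 0.87. The CMC correction therefore removes polymer mass but not bound water.

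**7. Dose wording.** Sections 5 and 6.2.4.11 can be read as one serving of 2.5 g CMC per day, while the Study Summary gives 15 g in six divided doses. At 2.5 g/day the fall would be 1% (200/202.5, k = 1) to 7% (100/107.5, k = 3).

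**The case against.** The strongest reply is that concentration is a legitimate estimand. A difference in concentration caused by the assigned diet is a true effect of assignment, so the t-test does not falsely reject its own null hypothesis. Section 6.4.3 values LPS and flagellin levels as reflecting what a specimen can provoke, which is a property of the specimen and not of daily output. This stands: only the further step to altered production is unsupported, and the protocol does not state that step.

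A reader might infer that CMC is known to enlarge the stool and that every fecal value must fall. The documents do not say so. Poor absorption is not the same as full recovery, and section 7.1 concerns detectability, not mass. A reader might also infer that all fecal assays are per gram. The word concentration is explicit only for metabolites; for the others it is inferred from stool samples being assayed, and the LPS/flagellin method is deferred to earlier publications.

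Nor do the documents show that weighing of the first stool is dropped after Day 1. Section 6.1.3 says all specimens are handled alike and that the sample weight is recorded, and section 6.2.6.5 refers back to earlier text. Whether that weight is the whole stool or the spoonful is unclear, so this is an ambiguity to settle.

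Finally, section 3.2 names no efficacy endpoint and the work is exploratory. That lowers the severity but does not remove the interpretive gap.

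**Conclusion.** The point holds as a cheap improvement. The planned analysis cannot separate dilution from changed production for fecal metabolites, and the same probably applies to fecal LPS, flagellin and lipocalin-2, whose denominators are not named. The direction is predictable if bulk is added: lower concentrations in the CMC arm.

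The size is uncertain and rests almost wholly on assumptions. Polymer alone gives a 7 to 13% fall, a shift of about 0.12 to 0.35 SD against the plan's detectable 1.51 SD. Bound water at 2 g per gram gives 18 to 31%, or 0.34 to 0.93 SD. A stronger reading, that the fecal results would be invalid or a signal wholly masked, is not supported; the documents contain no stool mass, recovery, water-binding or SD figure that would establish it. Plasma and serum results, taxon proportions and bacterial distance from the epithelium are not diluted in this way.

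**What to change.** 1. Keep the concentration t-test in section 7.2.2, and state the unit and denominator of each fecal assay in sections 6.4.3, 6.4.5 and 7.2.3.
2. Pre-specify a sensitivity analysis of daily output (concentration × total stool weight that day, averaged over named last on-diet days), and/or of concentration per gram of CMC-free stool from the section 6.4.2 assay. Output is preferable where bound water matters (step 6).
3. Report stool weight by arm.
4. Interpret a change as altered production only from the output or CMC-corrected result, with its confidence interval. Do not require both scales to agree in direction: they share the concentration noise. In simulation with dilution only, 56 to 100% of significant concentration results still agreed. With a true 1.5-fold rise and a dilution ratio of 0.53, such a rule cut detection by output from 33% to 11%.
5. Say in sections 6.1.3, 6.2.5.4 and 6.2.6.5 that the whole first stool is weighed on each inpatient day, as section 6.2.4.6 does for Day 1. Weights not taken cannot be recovered.
6. Reconcile the passages giving 15 g/day with those giving one 2.5 g serving per day.

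The cost is a few sentences and one or two derived variables per analyte, mostly from data already collected. Daily output is noisier, notably in people who do not pass stool every day, and it applies the first-stool concentration to later stools that are weighed but discarded. That is why it supplements the concentration analysis and does not replace it.

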4.4 Early Withdrawal of Participants

4.4.1 When and How to Withdraw Participants

Participants may be withdrawn from the study at any time if the investigator or the participant believes that the participant's safety will be jeopardized by continued participation, or if the participant does not follow study procedures. Likewise, participants will be withdrawn from the study if they withdraw consent.

5 Study Intervention

All foods will be prepared within the CHPS's metabolic kitchen without emulsifiers (unless specifically added). All participants will follow the same Western style diet (i.e. the only difference being portion size). The macronutrient percentages of calories for the study diet will be 55% carbohydrate, 30% fat, and 15% protein. The diet will be composed of two menus that will be consumed on alternating days. Water, coffee and tea will be provided as desired. Participants will have access to additional food outside of the meals provided, however, the entire serving of the previous meal must have been consumed. The additional food provided outside of the scheduled meals will consist of the food from the same Western style diet provided for each meal.

For the three days prior to admission, participants will be eating an emulsifier free diet at home. Food will be provided by the CHPS metabolic kitchen. After admission to CHPS, no emulsifiers will be consumed prior to dinner on Day 1. Thus, accounting for the 8 hours of nil per os status prior to admission, all participants will have approximately 80 hours of emulsifier free washout time prior to administration of the food containing CMC.

Participants will be randomly assigned to receive 0 or 15 gm per day of CMC (8 participants in each arm of the study). Beginning with the dinner meal on Day 1, all participants will consume one serving of brownie or sorbet (15 gm) per day that contain 0 or 2.5 gm CMC per serving. The brownie and sorbet servings will be provided at all three scheduled meals and scheduled snacks. Prior to eating any other food on the study menu, participants must consume the brownie and sorbet servings.

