6.2.2.3 Dietitian Evaluation

Caloric requirements will be estimated by the dietitian in the CHPS prior Visit 2 using standard methods to estimate metabolic requirements.³³ This will be completed prior to Visit 2 so that the CHPS metabolic kitchen can be prepared for the dietary needs of the participant prior to providing 3 days of outpatient emulsifier free food.. Participants who gain or lose weight will not have their food quantity adjusted to prevent further weight loss or gain as the effect of emulsifiers on body weight is one of the measures that the study will evaluate.

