6.2.4.1 History and physical exam

Vital signs (blood pressure should be done sitting) and weight will be recorded. Weight should be recorded with the participant wearing undergarments and a hospital gown prior to the first meal of the day. The patient should urinate prior to be weighed. Weight will be measured in triplicate. The participant should not be able to see the readout on the scale and should not be told their weight.

A complete physical exam and medical history will be completed to assess for abnormalities present at baseline and to confirm absence of intercurrent illnesses that would make the participant ineligible. Because the participants may be anxious on the first day of the inpatient stay, we will not use blood pressure on Day 1 as an exclusion criteria as long as the blood pressure at screening met the inclusion criteria (section 4.2).

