6.2.4.10 Recording of diet

Participants will begin their randomized diets following the oral glucose tolerance test and flexible sigmoidoscopy at dinner. Participants will be instructed to consume only the food provided and no other food. Participants must eat all of the brownie and servings of sorbet provided. Participants will have access to additional food outside of the meals provided, however, the entire serving of the previous meal must have been consumed. The amount of food consumed will be recorded on the case report forms.

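### The conditional regression in section 7.2.3 adjusts for Day 1 to Day 11 weight change as a confounder, but that change is a post-randomisation study outcome and should come out of the covariate list

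*Combined protocol and SAP*

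**What the plan says.** Section 7.2.3 of the combined protocol and SAP opens with weight as an outcome: "Weight change will be compared between the treatment groups from day 1 to day 11 using a t-test". The next sentence sets a condition, "If there is evidence of confounding despite randomization", and then the model: "additional analyses will use linear regression adjusted for change in weight from day 1 to day 11 and BMI at day 0". It does not say which outcomes the model serves or what counts as evidence of confounding. The rest of 7.2.3 compares satiety, glucose and insulin areas, beta-cell and insulin-resistance indices, hormones and cytokines by t-test. The glucose and insulin areas "at day 1, day 11 and the change from day 1 to day 11 will be compared between groups using a t-test".

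Other sections fix the role and timing of weight:

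- Section 6.2.2.3 leaves food quantity unadjusted when weight changes because "the effect of emulsifiers on body weight is one of the measures that the study will evaluate".
- Section 6.2.4.1, on Day 1: "Weight should be recorded with the participant wearing undergarments and a hospital gown prior to the first meal of the day".
- Section 6.2.4.10, on the start of exposure: "Participants will begin their randomized diets following the oral glucose tolerance test and flexible sigmoidoscopy at dinner".
- Section 5, on intake in both arms: "Participants will have access to additional food outside of the meals provided", provided the previous meal was finished.

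**The concern.** A confounder of a randomised comparison would have to be a chance imbalance present before exposure. Weight change to Day 11 is not that, because its second measurement follows exposure and the protocol lists it as something CMC may alter. Conditioning on it changes the quantity being estimated. If weight lies on the path from CMC to the outcome, adjustment removes that part of the effect. If weight change and the outcome share an unmeasured cause, adjustment can create an association that CMC did not produce.

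The practical risk is one of interpretation. The model is presented as a correction for confounding, so a reader who sees it differ from the t-test may conclude that the t-test was confounded. The t-test is in fact the estimate that randomisation protects.

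**Working it through.** **Timing.** The Day 1 weighing is before the first meal. The randomised diet starts at dinner, about 18:00 (section 6.2.4.11). The Day 11 weighing follows ten days of randomised diet. The covariate is Day 11 weight minus Day 1 weight, so it contains a post-exposure measurement.

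**Literal reading.** The regression sentence directly follows the weight-change t-test, with no other outcome in that paragraph. Taken at face value, weight change appears on both sides of the model. If the model instead extends to the Day 1 glucose and insulin comparisons, the covariate is completed ten days after the outcome.

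**The plan's own figure.** Section 7.1 gives 80% power at 1.51 SD with 8 per arm. Taking two-sided alpha of 0.05 (assumed, since 7.1 states none), the noncentrality is 1.51 × √(8/2) = 3.02 on 14 df, and power is 80.2%. The figure reproduces, and it belongs to the unadjusted t-test.

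**Model for the planned regression.** Outcome on arm, weight change and BMI; 16 participants minus 4 parameters leaves 12 df. In within-arm SD units:

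- weight change W = a × arm + e_w
- outcome Y = d × arm + e_y
- corr(e_w, e_y) = rho, with BMI taken as unrelated to the outcome

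The expected arm coefficient is d − rho × a, and the residual SD is √(1 − rho²). Neither a nor rho is in the documents; both are assumptions shown over a range. Power is from the noncentral t, averaged over simulated covariate draws.

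True total effect d = 1.51:

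| a | rho = 0.3: estimate, power | rho = 0.5: estimate, power |
|---|---|---|
| 0 | 1.51, 77% | 1.51, 84% |
| 0.2 | 1.51 − 0.06 = 1.45, 73% | 1.51 − 0.10 = 1.41, 78% |
| 0.5 | 1.51 − 0.15 = 1.36, 65% | 1.51 − 0.25 = 1.26, 67% |
| 1.0 | 1.51 − 0.30 = 1.21, 49% | 1.51 − 0.50 = 1.01, 43% |

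Not all the power loss is bias. At a = 1.0, collinearity between arm and weight change alone takes power to 67–75%; the shift in the estimate does the rest. If rho is negative the error reverses: at a = 0.5 the estimate is 1.66 to 1.76.

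Two limiting cases, rho 0.3 to 0.5:

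- No total effect (d = 0): the adjusted test rejects about 5% of the time at a = 0.2, 5.8–7.7% at a = 0.5 and 7.7–14.4% at a = 1.0. For Day 11 and change outcomes these rejections are spurious if a shared cause drives the correlation; otherwise they reflect a direct-effect estimand.
- Effect wholly through weight (d = rho × a, so 0.30 to 0.50 SD at a = 1.0): the adjusted estimate is 0 and rejection is about 5%. A real total effect vanishes from the adjusted result.

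**The case against.** The strongest defence is that little depends on this model. It is conditional and additional, the named comparisons in 7.2.3 are t-tests, section 3.2 sets no efficacy or safety endpoints, and no stated sample size, power or alpha changes. That stands, and it limits the point to the supporting regression.

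A second defence is that both arms eat the same diet apart from CMC, so weight may barely differ. At a = 0.2 the distortion is indeed small, and at a = 0 the planned model is unbiased and can gain power. But the documents do not bound a: extra food is available, portions are not corrected for weight change, and satiety is itself compared between arms.

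A third is that the model could be meant as mediation. Section 7.2.3 does not say so; it ties the model to confounding.

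Three stronger readings are tempting but not supported:

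- A reader might infer that the entire weight change arises under exposure. The Day 1 weighing precedes the first CMC serving by several hours, with the glucose drink, lunch and a snack scheduled in between. The supportable statement is that the Day 11 component is post-exposure, which is enough.
- A reader might infer that the Aim 3 results are biased. The t-tests do not use the covariate.
- A reader might take the rejection rates above as the trial's error rate. They describe only this model, if it is run, under assumed inputs.

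**Conclusion.** The point holds for the additional regression and should be fixed. Weight change from Day 1 to Day 11 cannot confound a randomised comparison, and the protocol treats it as an outcome. Taken literally the model is circular. Applied to other outcomes, it misses the total CMC effect by rho × a whenever CMC affects weight and weight change correlates with the outcome within arm. Over the assumed range (a from 0.2 to 1.0 SD, rho 0.3 to 0.5) that is 0.06 to 0.50 SD against a true 1.51 SD. The existence of the error follows from timing and does not rest on these inputs; its size and sign do.

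**What to change.** In section 7.2.3:

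1. Delete weight change from Day 1 to Day 11 as a confounder covariate.
2. Limit the additional regression to pre-exposure covariates. Baseline BMI qualifies once its time point is defined: the schedule in section 6.2 has no Day 0, and section 6.2.2.1 documents baseline BMI at screening.
3. Name the outcomes the regression covers, and replace the undefined trigger with a model specified in advance. For weight change as outcome, use baseline BMI alone.
4. State that the unadjusted t-test remains the main result.
5. Label any model containing weight change as exploratory mediation.

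Adding the outcome's Day 1 value is optional, and only for Day 11 or change outcomes that have one. Satiety has no Day 1 measurement.

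**Cost.** A few sentences and no new data. The t-tests are unaffected. For the additional model at 1.51 SD:

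- BMI alone gives about 77% power, against 80% for the t-test. If CMC does not affect weight, the planned model has about 73% to 84% at rho 0.1 to 0.5, so deletion can cost up to 84 − 77 = 7 points.
- With the Day 1 value added, a Day 11 outcome (1.51 Day 11 SDs) has about 73% at zero Day 1–Day 11 correlation, matches the t-test near 0.4 and reaches 84% at 0.5.
- For a change outcome (1.51 change-SDs) the pattern reverses: about 95% at zero correlation, 84% at 0.5 and 79–80% at 0.7.
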